Follow-up Testing – The participants will be followed over a 6-month period. One week (+/- 3 days) after the fitting the participants will be seen in the lab to re-verify the fit of their hearing aids and to determine any problems. The hearing aid use-time will be recorded from the data-logging system of the hearing aids as a reflection of hearing aid benefit and to document the extent to which the participants are wearing their hearing aids. During this session, both the aided and unaided portions of the APHAB will be administered along with the International Outcomes Inventory for Hearing Aids (IOI-HA; Cox & Alexander, 2002). In addition, the participants will answer a single question about their likelihood to continue hearing aid use. Intent to continue use tends to be related to user satisfaction with commercial products and service provision in other areas of healthcare. The participants also will complete the HHIA, and SSQ. The CCT, CRTT, CRTT-R and the phonetic context effect tasks will be re-administered with and without hearing aids.

Home Visits – The participants will be visited in their homes by study staff at three different times: 1-, 2- and 4-months post-fitting (+/- 1 week). The home visits will occur to reduce participant burden and encourage retention. However, some participants might prefer to be seen in the lab or clinic than their homes, and if that is the case those participants will be accommodated. Hearing aid use-time will be recorded from the data-logging system of the hearing aids and the hearing aids will be checked to determine appropriate function. During these visits the HHIA, SSQ, APHAB, IOI-HA, and the intent to continue use question will be re-administered. New hearing aid batteries will be provided and participants will be encouraged to wear their hearing aids for longer periods of time if their use-time is below 8 hours a day. At 6-months post-fitting (+/- 1 week) the laboratory follow-up testing will be repeated.

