Delayed-Treatment Control Group – The participants in the delayed-treatment control group will be selected from the mTBI-only group and followed over a 12-month period (+/- 2 weeks). At the onset of Part 2 they will complete the HHIA, SSQ, and the unaided portion of the APHAB. They will complete the speech perception and language tasks administered to the treatment group (CCT, phonetic context effect, and CRTT tasks) but unaided only. The delayed-treatment groups will receive home visits at 1, 2, 4 months (+/- 1 week) post-entry, at which times they will complete the HHIA, SSQ, and the unaided portion of the APHAB. At 6 months post-entry their pure tone hearing thresholds will be measured to determine possible changes in hearing sensitivity, and the procedures used with the treatment groups will be applied with the same sequence of follow-up sessions.

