and investigators, when possible, will participate in public events for veterans (e.g., Research Week, VA athletic events and fairs, Veteran's information tables at local university information and health fairs) where flyers and information will be offered about the study. Potential veterans can provide contact information at the time of the events if interested in participating in the study, or they can contact the study personnel at a later time. At the onset of the study and during Years 3 and 4, a review of audiology records in CPRS may be conducted for each site to identify possible participants based on target age range and normal or near normal pure tone audiometric test results. These individuals will be sent a letter describing the study and inviting them to contact local study personnel if they are interested in participating in the study. Also included in the mailing will be a stamped return envelope and a form that the veterans can return indicating that they would like to be contacted via telephone to discuss the study or opt-out and not be contacted about the study. Veterans who fail to return the form within 2 weeks will be contacted by telephone by study staff members to determine if they received the mailing. After the letters have been mailed, all information obtained from CPRS will be maintained in accordance with the VHA Records Control Schedule. Social Security Numbers will be used for CPRS access for recruitment, and then later for study data collection and subject payment purposed.

The significant others completing the HHIA-SO will be a family member or friend selected by the veteran participating in the study. The significant other is not required to complete or mail the questionnaire, and the veteran will not be penalized or withdrawn from the study if the questionnaire is not returned or if they do not have a person available or willing to complete the questionnaire.

Part 2

A subset of the participants from the mTBI-only and mTBI+PTSD groups from Part 1 will be selected to participate in Part 2. They will be placed into four groups of 25. The groups will consist of an mTBI-only treatment group and an mTBI+PTSD treatment group, along with an mTBI-only delayed-treatment control group and an mTBI+PTSD delayed-treatment control group.

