Primary Analyses – Basic descriptive statistics will be computed and examination of statistical assumptions will be performed for all study measurements. For questionnaire data, analysis of variance (ANOVA) or Kruskal Wallis test will be used to determine differences in the overall and subset scores between the mTBI groups. The analysis will also include basic descriptive statistics for behavioral data test measures at baseline and at 6 months for the mTBI-only and mTBI+PTSD groups, and at baseline and 12 months for the delayed-treatment groups. We will focus on the changes in the behavioral test measures from baseline to 6 months (mTBI-only and mTBI+PTSD treatment groups) and from baseline to 12 months (delayed-treatment groups). Specifically, paired t-test or Wilcoxon signed rank test will be used to determine change at 6 or 12 months and this test will be applied to each behavioral test measure separately. False discovery rate will be used to adjust the p-values for multiple hypotheses testing. All statistical analyses will be two sided and the significance level will be 0.05.

Secondary Analyses – For longitudinal analysis, the data will be modeled using linear-mixed models for which the outcome is the behavioral test measure across time. The predictors will include time, group and interaction between group and time. Covariates will be added to the model as needed. In addition, variables with a high Gini score from Part 1 will be correlated with final hearing aid results as a preliminary investigation of whether hearing aid benefit can be associated by any of the variables obtained above. We will measure correlations using either Pearson's or Spearman's correlation coefficient. We will adjust the p-values for multiple testing by using a false discovery rate method whenever more than one variable is being tested. Single-subject design metric also will be used to investigate individual responses to the hearing aid treatment.

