Sample Size and Power – This analysis will include data from 100 participants (25 for each group). For any comparisons of the four groups based on ANOVA with a significance level of 0.01 to account for multiple comparisons and a power of 0.80, an effect size of 0.38 or greater will be detectable. For the paired analyses described above, there is sufficient power (0.80) to detect an effect size of 0.50 (baseline versus 6 months) or 0.50 (baseline versus 12 months), or greater assuming a two-sided significance level of 0.01 to account for multiple comparisons. For the longitudinal modeling, there will be sufficient sample size to support the proposed modeling that will allow approximately 10 observations to be estimated for each parameter. The number of covariates in each model will depend on the sample size to insure that there are approximately 10 observations available for each parameter estimated. For correlation

based analyses, the study is powered (0.80) to detect correlations of 0.26 or greater in absolute value for a total sample size of 100.

Once the data are formatted and cleaned by a staff member at the VA Pittsburgh site under the supervision of the statistician, the data will be analyzed by the statistician.

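### Part 2 questionnaires get one between-group test with no time point or time origin, so for the instruments scored only after fitting neither the usable sample nor the question answered is defined

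*Combined protocol and SAP*

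**What the plan says.** Section 5.6, Part 2 Primary Analyses, gives the questionnaires one sentence: "For questionnaire data, analysis of variance (ANOVA) or Kruskal Wallis test will be used to determine differences in the overall and subset scores", comparing the mTBI groups. No instrument, visit or clock is stated. The paired tests that follow, and the linear mixed model under Secondary Analyses, are written for the behavioral test measures. Those measures do have stated times: baseline to 6 months for the treatment groups and baseline to 12 months for the delayed groups. Section 5.5 lists questionnaires and behavioral tests as separate kinds of assessment.

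Section 5.1 sets the collection schedule. After fitting, the treatment groups complete the aided and unaided APHAB, IOI-HA, intent item, HHIA and SSQ at one week. At the home visits, "the HHIA, SSQ, APHAB, IOI-HA, and the intent to continue use question will be re-administered", and the laboratory session is repeated at 6 months. Before fitting, the delayed participants are visited at 1, 2 and 4 months, "at which times they will complete the HHIA, SSQ, and the unaided portion of the APHAB". From 6 months post-entry they go through the treatment procedures and the same follow-up sequence.

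On group structure, section 5.2 says "They will be placed into four groups of 25": two treatment groups "along with an mTBI-only delayed-treatment control group and an mTBI+PTSD delayed-treatment control group". Section 5.1 says instead: "The participants in the delayed-treatment control group will be selected from the mTBI-only group". The power paragraph in 5.6 begins "For any comparisons of the four groups based on ANOVA with a significance level of 0.01" and gives a detectable effect size of 0.38 at 80% power.

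**The concern.** Objective (d) in section 3.0 asks whether these veterans perceive and demonstrate benefit from the hearing aids and whether PTSD influences it. Expected outcome (c) predicts that PTSD will restrict perceived benefit. The questionnaires carry the perceived part of that question.

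They fall into two kinds. HHIA, SSQ and unaided APHAB exist in every arm throughout. IOI-HA, aided APHAB (and so APHAB benefit) and intent to continue have no meaning until a person is fitted. A single between-group test cannot serve both kinds, and the plan does not separate them. Two things are at stake. The delayed arms exist to supply an unfitted comparison, but no questionnaire analysis is specified that isolates it. For the fitted-only instruments, the PTSD question would be tested either on half the sample or by an omnibus test that spends two of its three degrees of freedom on contrasts nobody has asked about.

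**Working it through.** **Which scores exist, and when (section 5.1)**

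| Instrument | Delayed arms before fitting | Delayed arms after fitting | Treatment arms after fitting |
|---|---|---|---|
| HHIA, SSQ | yes | yes | yes |
| APHAB, unaided | yes | yes | yes |
| APHAB, aided | no | yes | yes |
| IOI-HA, intent to continue | no | yes | yes |

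Month-6 pre-fitting scores for the delayed arms follow from section 5.1. The treatment procedures that start then include HHIA, SSQ and unaided APHAB before the fitting.

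**Inputs.** Four groups of 25, N = 100 (5.2, 5.6); alpha 0.01 and power 0.80 (5.6). The stated effect size is read as Cohen's f, since the plan does not name the metric.

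**Formula.** Power = P(F′ > F crit), where F′ is noncentral F with λ = N·f². For k groups the degrees of freedom are (k − 1, N − k). For two equal groups f = d/2.

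**1. The plan's own figure.** k = 4, N = 100, f = 0.38: λ = 100 × 0.1444 = 14.44 on (3, 96) df. Power is 72.9%, not 80%. The f detectable at 80% power is 0.405. A chi-square approximation gives 76.3% and 0.393, so 0.38 does not reproduce by either route. It is matched by three groups with N = 100 at alpha 0.01 (79.6%) or by four groups at alpha 0.02 (80.6%), but neither is the stated design.

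**2. Fitted-only instruments, timed from entry, before the delayed arms are fitted.** Only the two treatment groups have scores: 25 v 25, N = 50, df (1, 48). Detectable f = 0.50 (d about 1.00). At f = 0.38, λ = 50 × 0.1444 = 7.22 and power is 51%. At alpha 0.05 the detectable f is 0.40.

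**3. Fitted-only instruments, timed from fitting.** All 100 have scores and all are aided, so no hearing aid contrast remains. What can be tested is PTSD.

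Suppose a pure PTSD difference of d = 0.70, the same in both arms. Two group means lie d/2 above the grand mean and two lie d/2 below, so f = 0.35 and λ = 100 × 0.1225 = 12.25.

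- Four-group omnibus test, df (3, 96): power 63%.
- PTSD as one factor, 50 v 50, 1 df: power 81%; detectable f at 80% power is 0.35 (d about 0.70).

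The noncentrality is the same in both. The difference comes only from the degrees of freedom.

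**4. HHIA and SSQ at month 6 post-entry.** Fitted v not-yet-fitted is also 50 v 50 on 1 df, so the detectable f is again 0.35 before any gain from adjusting for the entry score. The plan gives no correlation from which to quantify that gain.

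**The case against.** A reader might infer that the plan intends a fitted-versus-unfitted ANOVA on IOI-HA and aided APHAB and so loses 50 of its 100 participants. The documents do not support that. Section 5.6 never describes the questionnaire test as fitted versus unfitted and sets no pre-fitting time point for it. If the timing given for the behavioral measures (6 months for treatment, 12 for delayed) were carried over, all 100 would have scores. The absence of an IOI-HA score before fitting belongs to the instrument and is not a collection error.

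Other points for the plan also have force. The phrase about the mTBI groups could mean mTBI-only against mTBI+PTSD, which is the right comparison for the fitted-only instruments. The sentence refers to overall and subset scores, so including the single intent item is an inference. The power statement is conditional on comparing four groups and is not tied to questionnaires. Section 5.2 calls Part 2 preliminary.

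These points limit the criticism without removing it. The wording allows several analyses that differ in sample, in clock and in the question answered. Under none of them is the unfitted control set out as a contrast for perceived benefit, although HHIA and SSQ would permit it. The planned correlations and single-subject metrics do not supply one either.

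**Conclusion.** The point stands as a specification fault with a better analysis available from data already planned. For IOI-HA, aided APHAB and intent to continue, the questionnaire test is either 25 v 25 (detectable f 0.50) or a comparison of 100 aided people that can inform on PTSD but not on benefit. For a PTSD effect of d = 0.70, moving from the omnibus to the 1-df test raises power from 63% to 81%. Separately, the stated 0.38 should be about 0.405.

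This rests on four assumptions: the effect size is Cohen's f; alpha is 0.01, as in the power paragraph, although the tests themselves are at 0.05 with false discovery rate adjustment; the PTSD difference is the same in both arms; and there are two delayed arms, as in section 5.2. If section 5.1 is right and delayed participants come only from mTBI-only, PTSD and arm are not crossed and the 50 v 50 figures do not apply. The month-6 comparison also assumes that treatment participants are fitted close to entry, an interval the plan does not state.

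**What to change.** In section 5.6:

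1. **HHIA and SSQ.** Compare fitted with not-yet-fitted arms at month 6 post-entry, using the delayed arms' pre-fitting scores, with PTSD group as a factor and the entry score as covariate. Treat unaided APHAB as supportive only: it rates listening without aids in both arms and is not a contrast of aided benefit.
2. **IOI-HA, aided APHAB and APHAB benefit, intent to continue.** Analyse at 6 months since fitting, pooling immediate and delayed arms. Test PTSD as a 1-df factor, include arm as a factor, and report the arm-by-PTSD interaction. State that this analysis does not estimate hearing aid benefit against an unfitted control.
3. **Power.** Replace 0.38 with about 0.405 for four groups, N = 100, alpha 0.01 (or state the design that gives 0.38). Add the 1-df figure of f = 0.35 (d about 0.70) for items 1 and 2.
4. **Groups.** Reconcile sections 5.1 and 5.2 on the delayed arms, since the 50 v 50 PTSD split depends on it.

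The cost is wording only, with no new visits or data. One small drawback is that item 2 pools people fitted about 6 months apart. The arm factor absorbs an average shift between them but not a PTSD effect that differs by arm, which is why the interaction should be reported.

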Using the order in which participants complete Part 2 as an identifier, the participants from the mTBI-only and mTBI+PTSD groups will be randomly assigned to receive either treatment or delayed treatment, and then ranked in random order for participation in Part 2. Each of the groups will be populated using this selection procedure. The assignments will be determined at the onset of the study by the PI with subsequent replacement as needed. Because Part 2 is preliminary in nature (not a randomized control trial) and includes low numbers of participants, any participants opting out of Part 2 will be replaced using the rank ordered list. Participants will be informed at the conclusion of Part 1 whether they can enroll in Part 2. If participants do not qualify, they will be informed that they could be contacted at a later date to act as a replacement. The study staff will be responsible for discussing enrollment in Part 2 with participants.

Payment

The veteran participants will be paid \$50 per session (laboratory and home visits) for their participation, and a \$25 travel allowance for each session requiring travel to one of the testing sites. They will be paid through the preferred method at each site (e.g., Financial Management System, vouchers, payment cards). When the Financial Management System is used the payment will not be immediate. The significant others who complete the HHIA-SO will not receive any payment.

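### Part 2 crosses randomised fitting with PTSD, but the only stated between-group questionnaire test compares four groups and isolates neither the fitting effect nor its dependence on PTSD

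*Combined protocol and SAP*

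**What the plan says.** Section 5.2 (Part 2) says of the participants: "They will be placed into four groups of 25". The groups are "an mTBI-only treatment group and an mTBI+PTSD treatment group, along with an mTBI-only delayed-treatment control group and an mTBI+PTSD delayed-treatment control group". Participants "will be randomly assigned to receive either treatment or delayed treatment". The same section calls Part 2 preliminary and says it is not a randomised controlled trial.

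Question d in Section 3.0 has two parts: whether these veterans benefit from mild-gain hearing aids, and whether PTSD influences that benefit. Expected outcome c predicts that PTSD will restrict perceived benefit.

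For Part 2 questionnaires, Section 5.6 states that "analysis of variance (ANOVA) or Kruskal Wallis test will be used to determine differences in the overall and subset scores between the mTBI groups". The Part 2 power text begins "For any comparisons of the four groups based on ANOVA with a significance level of 0.01 to account for multiple comparisons" and gives a detectable effect size of 0.38 at 80% power with 25 per group.

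The other Part 2 analyses concern behavioural test measures: paired tests of change, and a secondary mixed model with time, a single group factor and their interaction.

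Section 5.1 has the delayed groups complete the HHIA, SSQ and unaided APHAB at entry and at 1, 2 and 4 months. From 6 months they go through the same procedures as the treatment groups.

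**The concern.** Fitting is randomised and PTSD is observed, so the four groups form a 2 x 2 table. Question d corresponds to two 1-df effects in that table: the fitting effect and the fitting-by-PTSD interaction. The stated test asks only whether any of the four means differ. A significant result would not show whether the hearing aids, PTSD or both were responsible.

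Perceived benefit is measured by these questionnaires, and nothing else in the plan tests it between arms in a way that separates the two factors. Section 3.0 says the study should support a larger intervention study. An interpretable estimate of the fitting effect is therefore among the most useful things Part 2 can produce.

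**Working it through.** **Inputs.** From Sections 5.2 and 5.6: four groups, 25 each, N = 100, alpha 0.01, power 0.80, stated effect size 0.38. The scale is not named and is taken as Cohen's f. The documents give no expected effect, so every SD difference below is an assumption.

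**Method.** Noncentral F with 96 error df. For the four-group test, lambda = N x f², with 3 numerator df. For a 1-df contrast, lambda = (contrast / SE)², with these SEs in SD units:
- fitting effect (50 v 50): √(2/50) = 0.20
- fitting effect within one stratum (25 v 25): √(2/25) = 0.283
- difference in differences (interaction): √(4/25) = 0.40

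**1. The plan's own figure.** At f = 0.38, lambda = 100 x 0.38² = 14.44 and power is 0.729, not 0.80. Eighty per cent power needs lambda = 16.40, so f = √(16.40/100) = 0.405. Detecting f = 0.38 would take 29 per group (116 in all). With N = 100, alpha 0.01 and no covariate, 0.38 is reproduced only with 2 numerator df, that is three groups (f = 0.382).

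**2. PTSD difference only, no fitting effect, raw scores.** A difference d between strata gives f = d/2.

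| Assumed PTSD difference | Four-group test significant | 1-df fitting test significant |
|---|---|---|
| 0.3 SD | 7% | 1% |
| 0.5 SD | 28% | 1% |
| 0.8 SD | 79% | 1% |

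Simulation (20,000 runs per setting) agreed at 0.5 and 0.8 SD. With PTSD and fitting effects both at 0.5 SD, the four-group test rejected in 63% of runs, while the fitting effect itself was detected in 44%.

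**3. Fitting effect equal in both strata.** The four-group test needs d = 2 x 0.405 = 0.81 SD for 80% power. The 1-df fitting effect needs lambda = 12.09, so d = 0.20 x √12.09 = 0.70 SD. The ratio 16.40/12.09 = 1.36 means the four-group test needs about 36% more participants (34 v 25 per group). At 0.5 SD, power is 28% v 45%.

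**4. Fitting effect unequal between strata** (no PTSD effect in the delayed arms, alpha 0.01).

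| Benefit in the two strata | Four-group test | Fitting main effect |
|---|---|---|
| 0.8 / 0.8 SD | 79% | 91% |
| 0.8 / 0.4 SD | 56% | 65% |
| 0.8 / 0.2 SD | 55% | 45% |
| 0.8 / 0 SD | 62% | 27% |

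A planned contrast within the stratum that has a 0.8 SD benefit has lambda = 0.8²/0.08 = 8 and power 58%. That is close to the four-group test, and it also says which stratum benefits.

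**5. Detectable effects at 80% power.**

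| Effect | Alpha 0.01 | Alpha 0.05 |
|---|---|---|
| Fitting main effect | 0.70 SD | 0.57 SD |
| Fitting within one stratum (√2 x main effect) | 0.98 SD | 0.80 SD |
| Interaction (2 x main effect) | 1.39 SD | 1.13 SD |

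**The case against.** Several points on the other side have force.

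- **One-way is an inference.** That term appears only in the Part 1 text, and ANOVA can include factorial models. A reader might infer that the plan rules out factors or contrasts. It does not; it is silent. Naming Kruskal-Wallis as the alternative, together with the power wording "For any comparisons of the four groups based on ANOVA", makes the unstructured comparison the natural reading.
- **The PTSD difference is not quantified.** A reader might infer that a PTSD difference will make the test significant. Section 2.0 reports worse health, psychosocial function and quality of life with both conditions, but gives no figure for hearing questionnaires. Both mTBI groups are also selected on a hearing handicap score above 16 (Table 1), which may narrow any HHIA difference. So the documents support only that it can.
- **Change scores would largely remove that problem.** A stable PTSD difference cancels in change from baseline. Section 5.6 does not say which score or visit enters the ANOVA, so the rates in step 2 apply only to raw scores. Change scores would still not separate fitting from interaction.
- **The power loss is conditional.** A reader might infer that the four-group test always costs power for the hearing aid effect. Step 4 shows the reverse when benefit is largely confined to one stratum, and expected outcome c points partly that way.
- **Part 2 is labelled preliminary.** This limits how much weight any test should carry. It does not change the fact that assignment is random and that question d asks about two separate effects.

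**Conclusion.** The point holds in this form: the stated questionnaire test does not address either half of question d, and neither the paired tests nor the mixed model fills the gap. Both concern behavioural measures, and the mixed model's single group factor does not separate fitting from PTSD. This is a flaw of specification that should be corrected before analysis.

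Its practical size depends on two things the plan leaves open. With raw scores, false attribution to the hearing aid ranges from unlikely to very likely over the assumed PTSD differences. The advantage of a 1-df fitting test (0.70 v 0.81 SD detectable) rests on similar benefit in both strata. Separately, the stated 0.38 does not match four groups of 25 at alpha 0.01. All figures assume normal outcomes with equal variance and complete data.

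**What to change.** 1. For the HHIA, SSQ and unaided APHAB, replace the four-group test with a two-way model: fitting arm, PTSD stratum and their interaction. Use change from baseline or adjust for baseline, and name the visit. It must precede fitting of the delayed arms.
2. Pre-specify the fitting contrast within each PTSD stratum alongside the main effect. Use a rank-based or ordinal version of the same model in place of Kruskal-Wallis.
3. Report the IOI-HA and aided APHAB separately. The delayed arms do not complete them before fitting, so they have no unaided comparator. Confirm that the fitted arms complete the unaided APHAB at home visits, since Section 5.1 names only the APHAB there.
4. Restate the power text: 0.405 for any four-group test that is kept, 0.70 SD for the fitting effect and 1.39 SD for the interaction at alpha 0.01 (0.57 and 1.13 SD at alpha 0.05). Label the interaction exploratory. State which level governs, since the analysis text uses 0.05 and the power text 0.01.
5. Reconcile Section 5.1, which draws the delayed group from mTBI-only, with Section 5.2, which has delayed groups in both strata. The two-way model depends on the latter.

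The cost is SAP wording and restated figures, with no new data or participants. The downside is less power for the fitting main effect than for the four-group test if benefit is largely limited to one stratum; the within-stratum contrasts address this.

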Standardized fitting and verification procedures consistent with the American Academy of Audiology guidelines for audiology management of adult patients will be used. The hearing aids will be obtained through the VA hearing aid procurement procedures because the participants qualify for hearing aids due to their auditory impairment. High-end behind-the-ear hearing aids (Phonak Bolero Q90) will be fitted binaurally. The hearing aids will provide mild gain with high-frequency emphasis, which will be verified acoustically with real ear measures. The noise suppression circuitry of the hearing aids will be activated but the frequency compression or shifting will be deactivated.

Additionally, to reduce the risk of sounds being too loud for the participants, Maximum Power Output will be set below the loudness discomfort levels of the participants.

Prior to their hearing aid fitting the participants in the two treatment groups will complete the unaided portion of the Abbreviated Profile of Hearing Aid Benefit (APHAB, Cox & Alexander, 1995), along with the HHIA, and SSQ as pretreatment measures of self-perceived hearing handicap, and situational hearing skills. To assess pre-fitting speech perception and language processing the California Consonant Test (CCT; Owens & Schubert, 1997) will be administered in the sound field at 65 dB HL in quiet and with multi-talker babble.

Recovery of co-articulation (phonetic context effect) will be measured with a vowel identification task. The vowels will be presented in the context of /d/ and /b/ sounds (Holte & Lotto, 2006). The extent to which the consonant context changes the perception of vowel categories will be measured.

As in Part 1 of the study, sentence level processing will be measured with the auditory and reading versions of subtests 1 through 10 from the Computerized Revised Token Test (CRTT and CRTT-R respectively) and will be administered in quiet and in babble to assess sentence level processing in both auditory and reading domains in optimal and adverse acoustic conditions.

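### The only group comparison stated for the Part 2 questionnaires has no baseline term, although HHIA, SSQ and unaided APHAB are collected before treatment in all four groups

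*Combined protocol and SAP*

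**What the plan says.** Section 5.6, Part 2 Primary Analyses, says of the questionnaires that "analysis of variance (ANOVA) or Kruskal Wallis test will be used to determine differences in the overall and subset scores between the mTBI groups". It does not say whether the scores are raw or changes from baseline, or at which visit they are taken. The sentences that follow turn to behavioural tests and specify change from baseline by paired t-test or signed rank test. The Secondary Analyses add a linear mixed model with group, time and their interaction, but its outcome is again a behavioural test, and the remark about adding covariates belongs to that model. ANCOVA, with a non-parametric alternative, is planned for Part 1 and is not mentioned for Part 2.

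Section 5.1 shows that baseline scores exist. Before fitting, the treated groups complete unaided APHAB "along with the HHIA, and SSQ as pretreatment measures of self-perceived hearing handicap, and situational hearing skills". Of the delayed group it says: "At the onset of Part 2 they will complete the HHIA, SSQ, and the unaided portion of the APHAB". After fitting, the same instruments are repeated with two new ones: "During these visits the HHIA, SSQ, APHAB, IOI-HA, and the intent to continue use question will be re-administered".

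For sizing, section 5.6 takes a four-group "ANOVA with a significance level of 0.01 to account for multiple comparisons and a power of 0.80" and concludes that "an effect size of 0.38 or greater will be detectable".

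**The concern.** Study question d (section 3.0) asks whether veterans perceive benefit from the aids and whether PTSD influences it. The questionnaires are the direct measure of perceived benefit. A one-way test on follow-up scores gives up the precision that a pretreatment score on the same scale provides, and with 25 per group precision is scarce.

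The four groups also combine two different factors. Immediate versus delayed treatment is randomly assigned within each mTBI group (section 5.2). PTSD status is an observed characteristic. If the PTSD groups score differently before any aid is fitted, a follow-up comparison without baseline carries that difference forward, and it can be taken for PTSD changing the benefit.

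**Working it through.** **Inputs.** Four groups of 25, N = 100; alpha 0.01 and power 0.80 for sizing; testing at two-sided 0.05 with false discovery rate adjustment (all section 5.6). The correlation r between baseline and follow-up score is not in the documents, so 0.3 to 0.7 is assumed (0.8 is added in steps 3 and 4). The 0.38 is read as Cohen's f. The four-group allocation follows sections 5.2 and 5.6.

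**1. The plan's own figure.** One-way ANOVA, noncentral F, df 3 and 96, noncentrality N·f². At alpha 0.01, f = 0.38 gives 100 × 0.38² = 14.44 and power 72.9%. The f detectable with 80% power is 0.405, so 0.38 does not reproduce. At unadjusted alpha 0.05, power at 0.38 is 89%.

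**2. Precision.** A baseline covariate multiplies residual variance by 1 − r². At r = 0.5 this is 0.75, worth 1/0.75 = 1.33 times the sample. For the four-group test the noncentrality becomes N·f²/(1 − r²) with df 3 and 95.

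Question d needs 1-df terms. With outcome SD 1, the treatment effect (50 v 50) has SE √(1/50 + 1/50) = 0.20. The treatment-by-PTSD interaction, a difference of two differences, has SE √(4/25) = 0.40. Both are multiplied by √(1 − r²). The detectable effect comes from the noncentral F with 1 and 95 df (96 without the covariate) and noncentrality (effect/SE)².

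Detectable at 80% power, alpha 0.01:

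| r | 1 − r² | four-group f | treatment effect, SD | interaction, SD |
|---|---|---|---|---|
| no baseline term | 1.00 | 0.405 | 0.70 | 1.39 |
| 0.3 | 0.91 | 0.386 | 0.66 | 1.33 |
| 0.5 | 0.75 | 0.351 | 0.60 | 1.20 |
| 0.6 | 0.64 | 0.324 | 0.56 | 1.11 |
| 0.7 | 0.51 | 0.289 | 0.50 | 0.99 |

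**3. Chance gaps in the randomised contrast.** The baseline difference between two groups of 25 has SE √(2/25) = 0.283 SD, so 95% of gaps lie within ±1.96 × 0.283 = ±0.55 SD. Gaps above 0.3 SD occur in 29% of pairs and above 0.5 SD in 7.7%. An unadjusted comparison carries over r times the gap; at the 95% limit that is 0.28 SD (r = 0.5) to 0.39 SD (r = 0.7).

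Given a gap g and no treatment effect, the follow-up difference is normal with mean r·g and variance (2/25)(1 − r²). With g = 0.5, the conditional false-positive rate of a nominal 5% test is 9.7%, 13.9% and 16.0% at r = 0.5, 0.7 and 0.8. With g = 0.3 it is below 5% (4.5%, 3.8%, 2.6%). Averaged over all randomisations it is nominal.

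**4. A systematic gap between PTSD groups.** Suppose, for illustration, that the PTSD groups start 0.5 SD apart and nothing changes. The four means are 0, 0, 0.5, 0.5, so f = 0.25 and the noncentrality is 100 × 0.0625 = 6.25. The four-group ANOVA then rejects in about 28% of trials at alpha 0.01 and 52% at 0.05. The gap is the same in treated and delayed participants, so it cancels from both the treatment effect and the interaction. ANCOVA removes only r times the gap from the PTSD main effect: (1 − r) × 0.5 remains, which is 0.25, 0.15 and 0.10 SD at r = 0.5, 0.7 and 0.8.

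**The case against.** A reader might infer that the plain ANOVA lets a PTSD-related gap pass for a hearing aid effect. The documents do not support that. Assignment to treatment or delay is random within each mTBI group, 25 per cell, so such a gap is expected equally in both arms; only chance imbalance remains for the treatment contrast, and the nominal test allows for it. Replacement of participants who opt out (section 5.2) weakens this protection somewhat, but does not create a known bias.

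Nor do the documents say that baseline questionnaire scores differ by PTSD. The expected outcomes concern severity of deficits and restricted benefit, and both mTBI groups enter on the same handicap cut-off (Table 1). The gap in step 4 is a possibility, not a finding.

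It can also be said that the text leaves open whether scores are raw or changes, that power at f = 0.38 is adequate at unadjusted 0.05, and that section 5.2 calls Part 2 preliminary and not a randomised controlled trial. The first stands: the defect is an unspecified analysis, although the contrast with the explicit change analyses of behavioural tests favours raw scores. The second shows that low power depends on the alpha used; the relative gain from adjustment does not. The third limits how much weight the point carries, but small groups are where a baseline covariate helps most.

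Finally, ANCOVA is not a complete cure for a non-randomised comparison, as step 4 shows. This stands and shapes the fix.

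**Conclusion.** The point holds as a gap in specification with a real but moderate cost. No stated group comparison of the Part 2 questionnaires uses the pretreatment HHIA, SSQ or unaided APHAB. For treatment versus delay, the loss is precision (25% of residual variance at r = 0.5, 49% at r = 0.7) and exposure to chance gaps with SE 0.28 SD between two groups; overall type I error is sound. For PTSD, a pre-existing gap could be misread as PTSD altering benefit.

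The size rests on the assumed r and on four groups of 25. Even with adjustment, the interaction is detectable at alpha 0.01 only if it is about 1.0 to 1.3 SD, so a null result on PTSD's influence would be weak evidence. It should not be inferred that every questionnaire can be adjusted: IOI-HA and the intent-to-continue question are first given after fitting. The failure of 0.38 to reproduce at alpha 0.01 is a separate sample-size error and adds nothing to this point.

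**What to change.** In section 5.6, Part 2 Primary Analyses:

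- For HHIA, SSQ and APHAB, replace the plain ANOVA with an ANCOVA of the 6-month score on treatment (immediate v delayed), PTSD group, their interaction and the Part 2 pretreatment score of the same questionnaire. Use a rank-based ANCOVA as fallback in place of Kruskal-Wallis. State which APHAB portion is the treated groups' 6-month outcome.
- Judge the hearing aid effect from the treatment term and PTSD's influence on benefit from the interaction, not from the PTSD main effect.
- Extend the planned group-by-time mixed model to these questionnaires, to describe change by PTSD group.
- Leave IOI-HA and the intent-to-continue question unadjusted.
- Restate the detectable effects for the 1-df terms over a range of assumed r, as in the table.

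In section 5.1, Delayed-Treatment Control Group, state that HHIA, SSQ and unaided APHAB are completed at 6 months before fitting. At present this is only implied by applying the treatment-group procedures from that point. The same paragraph draws the delayed group from mTBI-only participants, while section 5.2 has a delayed group for each PTSD stratum; the two must be reconciled, because the interaction needs both.

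The cost is one degree of freedom and revised wording. No instrument is added; the 6-month scores of the delayed groups are implied already but need to be made explicit.
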